### 8.3.2 DEFINITION OF SERIOUS ADVERSE EVENTS (SAE)

An adverse event (AE) or suspected adverse reaction is considered "serious" if, in the view of either the investigator or sponsor, it results in any of the following outcomes: death, a life-threatening adverse event, inpatient hospitalization or prolongation of existing hospitalization, a persistent or significant incapacity or substantial disruption of the ability to conduct normal life functions, or a congenital anomaly/birth defect. Important medical events that may not result in death, be life-threatening, or require hospitalization may be considered serious when, based upon appropriate medical judgment, they may jeopardize the participant and may require medical or surgical intervention to prevent one of the outcomes listed in this definition.

### 8.3.3 CLASSIFICATION OF AN ADVERSE EVENT

#### 8.3.3.1 SEVERITY OF EVENT

For adverse events (AEs) not included in the protocol defined grading system, the following guidelines will be used to describe severity.

- **Mild** – Events require minimal or no treatment and do not interfere with the participant's daily activities.
- **Moderate** – Events result in a low level of inconvenience or concern with the therapeutic measures. Moderate events may cause some interference with functioning.

- **Severe** – Events interrupt a participant’s usual daily activity and may require systemic drug therapy or other treatment. Severe events are usually potentially life-threatening or incapacitating. Of note, the term “severe” does not necessarily equate to “serious”.

### 8.3.3.2 RELATIONSHIP TO STUDY INTERVENTION

All adverse events (AEs) must have their relationship to study intervention assessed by the study staff. The degree of certainty about causality will be graded using the categories below. In a clinical trial, the study product must always be suspect.

- **Related** – The AE is known to occur with the study intervention, there is a reasonable possibility that the study intervention caused the AE, or there is a temporal relationship between the study intervention and event. Reasonable possibility means that there is evidence to suggest a causal relationship between the study intervention and the AE.
- **Not Related** – There is not a reasonable possibility that the administration of the study intervention caused the event, there is no temporal relationship between the study intervention and event onset, or an alternate etiology has been established.

### 8.3.3.3 EXPECTEDNESS

The Principle Investigator will be responsible for determining whether an adverse event (AE) is expected or unexpected. An AE will be considered unexpected if the nature, severity, or frequency of the event is not consistent with the risk information previously described for the study intervention.

### 8.3.4 TIME PERIOD AND FREQUENCY FOR EVENT ASSESSMENT AND FOLLOW-UP

The occurrence of an adverse event (AE) or serious adverse event (SAE) may come to the attention of study personnel during study visits and interviews of a study participant upon review by a study monitor.

All AEs including local and systemic reactions not meeting the criteria for SAEs will be captured on the appropriate case report form (CRF). Information to be collected includes event description, time of onset, clinician’s assessment of severity, relationship to study product (assessed only by those with the training and authority to make a diagnosis), and time of resolution/stabilization of the event. All AEs occurring while on study must be documented appropriately regardless of relationship. All AEs will be followed to adequate resolution.

Changes in the severity of an AE will be documented to allow an assessment of the duration of the event at each level of severity to be performed. AEs characterized as intermittent require documentation of onset and duration of each episode.

The Clinical Research Coordinator will record all reportable events with start dates occurring any time after informed consent is obtained until the last day of study participation. Events will be followed for outcome information until resolution or stabilization.

### 8.3.5 ADVERSE EVENT REPORTING

The Primary Investigator will immediately report to the sponsor any adverse event, whether or not considered study intervention related, including breach of confidentiality or lack of safety whether there is a reasonable possibility that the study intervention caused the event. All adverse events (AEs) will be followed until satisfactory resolution or until the site investigator deems the event to be chronic or the participant is stable. Other supporting documentation of the event may be requested by the study sponsor and should be provided as soon as possible.

### 8.3.6 SERIOUS ADVERSE EVENT REPORTING

The Primary Investigator will immediately report to the sponsor any serious adverse event including lack of safety whether there is a reasonable possibility that the study intervention caused the event. All serious adverse events (SAEs) will be followed until satisfactory resolution or until the site investigator deems the event to be chronic or the participant is stable. Other supporting documentation of the event may be requested by the study sponsor and should be provided as soon as possible.

### 8.3.7 REPORTING EVENTS TO PARTICIPANTS

Not Applicable

### 8.3.8 EVENTS OF SPECIAL INTEREST

Not Applicable

### 8.3.9 REPORTING OF PREGNANCY

Not Applicable

## 8.4 UNANTICIPATED PROBLEMS

### 8.4.1 DEFINITION OF UNANTICIPATED PROBLEMS (UP)

The Office for Human Research Protections (OHRP) considers unanticipated problems involving risks to participants or others to include, in general, any incident, experience, or outcome that meets **all** of the following criteria:

- Unexpected in terms of nature, severity, or frequency given (a) the research procedures that are described in the protocol-related documents, such as the Institutional Review Board (IRB)-approved research protocol and informed consent document; and (b) the characteristics of the participant population being studied;
- Related or possibly related to participation in the research (“possibly related” means there is a reasonable possibility that the incident, experience, or outcome may have been caused by the procedures involved in the research); and
- Suggests that the research places participants or others at a greater risk of harm (including physical, psychological, economic, or social harm) than was previously known or recognized.

#### 8.4.2 UNANTICIPATED PROBLEM REPORTING

The Primary Investigator will report unanticipated problems (UPs) to the reviewing Institutional Review Board (IRB). The UP report will include the following information:

- Protocol identifying information: protocol title and number, PI's name, and the IRB project number;
- A detailed description of the event, incident, experience, or outcome;
- An explanation of the basis for determining that the event, incident, experience, or outcome represents an UP;
- A description of any changes to the protocol or other corrective actions that have been taken or are proposed in response to the UP.

To satisfy the requirement for prompt reporting, UPs will be reported using the following timeline:

- UPs that are serious adverse events (SAEs) will be reported to the IRB and to the study sponsor within 7 days of the investigator becoming aware of the event.
- Any other UP will be reported to the IRB and to the study sponsor within 14 days of the investigator becoming aware of the problem.
- All UPs should be reported to appropriate institutional officials (as required by an institution's written reporting procedures), the supporting agency head (or designee), and the Office for Human Research Protections (OHRP) within 7 days of the IRB's receipt of the report of the problem from the investigator.

#### 8.4.3 REPORTING UNANTICIPATED PROBLEMS TO PARTICIPANTS

Not Applicable

### 9 STATISTICAL CONSIDERATIONS

#### 9.1 STATISTICAL HYPOTHESES

Primary Endpoint: MKit is safe, usable, acceptable, and participants will be willing to use it.

Secondary Endpoint: To explore preliminary differences between the intervention and control groups in regards to retention, knowledge, attitudes, and experiences related to sexual and intimate partner violence.

#### 9.2 SAMPLE SIZE DETERMINATION

Formal sample size calculations were not performed because this is a pilot feasibility study. The number of subjects was chosen based on feasibility and is considered sufficient to meet the study objectives.

### 9.3 POPULATIONS FOR ANALYSES

All data collected through the pilot study process will be utilized for the analyses related to feasibility, usability, and acceptability. The data collected from the semi-structured interview subjects will be utilized to analyze the safety of the application and the willingness of participants to use the application.

### 9.4 STATISTICAL ANALYSES

#### 9.4.1 GENERAL APPROACH

The survey data will be analyzed using the Statistical Package for the Social Sciences (SPSS); all p-values will be set at  $<.05$ . Descriptive statistics will be assessed first. The baseline, 1-month post, and 5-month post-intervention tests will be examined for measures of central tendency, measures of dispersion, and frequency distribution on outcomes. Analysis of variance (ANOVA) will be utilized to determine if the scores on the baseline and follow-up tests differ significantly among the two arms. Usability and acceptability scores will be assessed among those in the intervention group.

We are not powered to assess outcome measures (sexual violence experiences/behaviors, rape myth acceptance, or sexual relationship power); however, we will look at the direction of effects for our outcome measures to allow for power calculations for a future R-Level submission. The results of this project will establish the safety and usability of this adapted web-based application for future scale-up.

For the semi-structured interviews, all audiotapes will be transcribed verbatim. Data analyses will be conducted using an iterative process and the constant comparative method of analysis (Glaser, 1992). Member checking will contribute to credibility through validation of the research findings by participants. A codebook will be developed after repeated high-level reading of the transcripts by the study team. Data will be coded and grouped into categories to facilitate abstraction and concept analysis.

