**Endpoints:**

- Primary: Safety (qualitative interviews), Usability (System Usability Scale, Brooke, 1986), Acceptability (investigator generated), and willingness to use (qualitative interviews).
- Secondary: Retention (percent completing follow-up surveys), Sexual and Intimate Partner Violence Knowledge (adapted from Texas Education Program Participant Response Form), Self-Efficacy of Protective Behaviors Related to Sexual and Intimate Partner Violence (investigator generated), Intimate Partner Violence Attitude Scale (adapted from Finchman, Cuit, Braithwaite, & Pasley, 2008), Consensual Sexual Activity (investigator generated), Sexual victimization/perpetration (Sexual Experiences Survey, Koss et al., 2007), and Universal Violence Prevention Screening (adapted from Heron, Thompson, Jackson, & Kaslow, 2003).

**Study Population:** 300 first year university students (150 Control Group, 150 Intervention Group)

[figure not shown]
**Phase:** Pilot

**Description of  
Sites/Facilities  
Enrolling  
Participants:**

University of Michigan Residence Halls (Alice Lloyd and Couzens)

Description of Study Intervention:	Web-based app that uses a life skills approach to address healthy relationships and sexual violence.
Study Duration:	2 years 9 months
Participant Duration:	For pilot study – 6 months

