### 2.2 BACKGROUND

With a national annual incidence rate of 5%, rape is the most frequent violent crime that occurs on college campuses (Finn, 1995; Fisher, Cullen, & Turner, 2000). Nearly 80-90% of college students know the perpetrator, which increases the likelihood that the rape will be completed, rather than attempted (Fisher et al., 2000; Karjane, Fisher, & Cullen, 2005). Furthermore, many college survivors do not perceive or acknowledge their experiences as a rape, often because of lack of evidence, the absence of a weapon, or because alcohol and/or drugs were involved (Fisher, Daigle, Cullen, & Turner, 2003; Karjane et al., 2005). These characteristics of sexual assault in college therefore contribute to the underestimation, under reporting, under prosecution, and low rates of seeking post-assault services among college survivors (BonDurant, 2001; Karjane et al., 2005).

Despite the high prevalence of rape in the United States, an event with long-term negative effects on a survivor's health, few survivors receive comprehensive post-assault care. In the period immediately following a rape, about half of all survivors will have evidence of physical trauma, up to 30% contract a sexually transmitted infection (STI), and 5% of female survivors become pregnant (Resnick et al., 2000). Specific to college survivors, about 20% report physical injuries (Fisher et al., 2000), many fear social consequences so they alienate themselves from campus activities or drop out of school, and it appears that college women who experience post-traumatic stress disorder (PTSD) from an assault may use substances and/or sexual behavior to reduce distress (Messman-Moore, Ward, & Brown, 2009). Post-assault, survivors can access comprehensive health services through referral by rape crisis centers or via the emergency department from specially trained sexual assault nurse examiner (SANE) programs. Comprehensive care includes 1) treatment of physical injuries or other sequelae of the assault, 2) pregnancy prevention, including options if emergency contraception is not effective, 3) STI screening and treatment, 4) psychological care for PTSD, 5) forensic and victim services, and 6) legal care, including safety from the perpetrator and the ability to report the assault and press

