The Control group will only receive the usual care delivered to all incoming University of Michigan students, which includes Haven (an online course about sexual violence), Relationship Remix (an interactive program about healthy relationships and sexual violence delivered by peers), and Change it Up (a theater based performance on bystander intervention). The Intervention group will receive the usual care described above as well as access to MKit. They will be encouraged to interact with MKit throughout the study. Data will be collected on the content viewed by the participants, as well as the amount of time they spend within each content area, and the order in which they view the content.

At 1 and 5 months, we will repeat all baseline measures in both groups. Participants in the Intervention group will also be asked to complete the 10-item System Usability Scale (Brooke, 1996) and an investigator created 5-item acceptability scale.

Post-intervention semi-structured interviews will be conducted with 25 participants, including 15 participants from the intervention group and 10 participants from the control group, to assess perceived safety, reaction to content, desirability, willingness to continue using the content, and willingness to recommend the content to others. Prior to commencing the interviews, we will ask each participant to complete a paper demographic survey.

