## 7 STUDY INTERVENTION DISCONTINUATION AND PARTICIPANT DISCONTINUATION/WITHDRAWAL

### 7.1 DISCONTINUATION OF STUDY INTERVENTION

All participation is voluntary. There is no penalty to anyone who decides not to participate or who wishes to end participation during the study. All participants may choose not to answer a question at any point in the study.

If a participant discontinues use of the intervention during the research study, their data will be retained for attrition analyses.

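### ANOVA of unstated type is the only method named for the three-wave scale scores, with no rule for skipped items or missed waves and no allowance for violence-related non-response

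*Combined protocol and SAP*

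**What the plan says.** Section 9.4.1 plans descriptive statistics at baseline, 1 month and 5 months, and then: "Analysis of variance (ANOVA) will be utilized to determine if the scores on the baseline and follow-up tests differ significantly among the two arms". Section 9.4.3 says the same for knowledge, attitudes and experiences. Neither states whether the ANOVA is repeated-measures, per-wave or on change scores.

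The measures are collected three times (Section 4.1: "At 1 and 5 months, we will repeat all baseline measures in both groups"). Section 3 gives their lengths: 34 items for attitudes, 26 for intimate partner violence, 20 for knowledge, 15 for self-efficacy, and 10 each for sexual victimization and perpetration.

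Skipping is allowed by design. Section 7.1 says: "All participants may choose not to answer a question at any point in the study". Sections 2.3.1 and 7.2 say the same in substance.

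On loss to follow-up, Sections 7.1 to 7.3 keep the data of students who stop, withdraw or are lost, for use in attrition analyses. Section 9 does not describe those analyses. Section 9.3 defines no analysis population for knowledge, attitudes or experiences. Section 2.2 says of college survivors that "many fear social consequences so they alienate themselves from campus activities or drop out of school".

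The secondary results have a stated use: "we will look at the direction of effects for our outcome measures to allow for power calculations for a future R-Level submission".

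**The concern.** Two separate problems arise.

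The first is lost scores. With long scales, permitted skipping and three waves, some incomplete scores are foreseeable. With no rule, software defaults decide. Plain addition of items makes a total missing if one item is missing, while summing only the answered items treats a skip as zero. A repeated-measures ANOVA then removes a student who lacks any one wave.

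The second is selective response. Section 2.2 gives a reason why students who experience violence might stop responding. If they do, the 5-month rates among responders understate the truth.

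The secondary outcomes are openly unpowered, so no hypothesis test is at risk. What is at stake is the means, SDs and event rates. Sections 3 and 4.2 treat obtaining data for the next trial's power calculation as a key part of this study.

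**Working it through.** The plan has no figure to reproduce. Section 9.2 says: "Formal sample size calculations were not performed because this is a pilot feasibility study". It also gives no skip rate and no expected dropout, so every rate below is an assumption shown over a range.

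**Complete scores.** Let k be the number of items (Section 3), s the skip probability per item, and suppose that any skip voids the score. With independent skips, the share complete is (1−s)^k at one wave and (1−s)^(3k) over three waves. For clustered skips a beta-binomial with within-person correlation rho replaces this. For the 34-item attitude scale (3k = 102):

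| Skip rate | Pattern | One wave | Three waves |
|---|---|---|---|
| 0.1% | independent | 97% | 90% |
| 0.5% | independent | 84% | 60% |
| 1% | independent | 0.99^34 = 71% | 0.99^102 = 36% |
| 1% | rho 0.1 | 87% | 79% |
| 1% | rho 0.3 | 93% | 91% |
| 2% | independent | 50% | 13% |

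Shorter scales lose less. At 1% independent skipping, three-wave completeness is 46% for 26 items and 74% for 10 items.

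**Students analysed per arm.** Assume 80% retention at 5 months, that everyone present at 5 months also answered at 1 month, and 1% independent skips on the 34-item scale:

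- Repeated-measures ANOVA, listwise: 150 × 0.80 × 0.359 = 43.
- Per-wave ANOVA at 5 months: 150 × 0.80 × 0.711 = 85.
- Per-wave ANOVA with prorating that rescues every score: 150 × 0.80 = 120.

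With clustered skips (rho 0.1), the first figure becomes 120 × 0.794 = 95. A mixed model would also use the earlier waves of students who leave.

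**Violence rates.** Let p be the true rate, r1 the retention of affected students and r0 that of others. The rate among responders is p·r1 / [p·r1 + (1−p)·r0]. Take p = 5%, the national annual rape incidence in Section 2.2. It is only an illustration, because the planned measures are broader and the follow-up is five months. With r0 = 80%:

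- r1 = 80%: 5.0%, no bias.
- r1 = 70%: 0.035 / 0.795 = 4.4%.
- r1 = 60%: 0.030 / 0.790 = 3.8%.
- r1 = 40%: 0.020 / 0.780 = 2.6%.

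The relative error depends little on p. With r1 = 60%, the observed rate is 76%, 77% and 79% of the truth at p = 5%, 10% and 20%.

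**Effect on the next trial.** To detect a halving (two-sided 0.05, 80% power, before any cluster inflation), the sample size per arm is 906 at 5.0%, 1,203 at 3.8% and 1,804 at 2.6%. On that basis, an understated rate makes the next trial look larger than it needs to be.

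**The case against.** A reader might infer that the plan commits to a three-wave, complete-case ANOVA, that many scores will therefore be lost, and that the violence rates will be biased low. The documents do not support any of these as stated.

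- The plan never says repeated-measures or complete-case. Per-wave or change-score ANOVA fits the wording equally well and does not need all three waves.
- The 36% figure needs independent skips and a rule that one skip voids the score. Neither is in the plan, and skips may well cluster in the same people.
- ANOVA does not cause the selective-response problem. The per-wave descriptive tables, which are the natural source of SDs and rates, would be affected in the same way.
- Section 2.2 gives no dropout rate or time frame, and a student who withdraws from campus life can still answer an online survey. With equal retention there is no bias.
- Attrition is not ignored. Section 7 retains data for attrition analyses, retention is a secondary endpoint, and Section 9.1 compares it between arms.

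All of this stands and limits how strongly the point can be put. It does not remove the point. Keeping data for an attrition analysis is not a method, and Section 9 assigns it no role in the secondary estimates. Which ANOVA is meant, and how a partly answered scale is scored, remain open. A method that uses the available data better can be had without new data collection.

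**Conclusion.** The concern holds in a conditional form. The plan names one method, of unspecified type, for three-wave scores and says nothing about skipped items or missed waves. The loss could be slight or severe. Three-wave completeness on the 34-item scale is about 36% to 91% at 1% skipping, depending on clustering, and about 90% at 0.1% independent skipping, in each case if any skip voids a score.

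The violence rates could be too low if affected students respond less often. In the illustration, 60% against 80% retention turns 5.0% into 3.8%. That retention gap is an assumption. A distorted comparison between arms would further require retention to differ by arm. The matter is minor for this pilot's conclusions and matters mainly for the figures carried into the next trial.

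**What to change.** - **Knowledge, self-efficacy and attitudes:** replace ANOVA with a linear mixed model on every available wave (SPSS MIXED). Prorate a scale from the student's mean of answered items when a pre-set minimum share, for example 80%, is answered. The threshold is a choice; what matters is fixing it in advance. The model corrects for missed waves only so far as the observed data explain them.
- **Experience outcomes:** write the attrition analysis promised in Section 7 into Section 9, as 5-month completion by what the student reported at baseline and at 1 month, and by arm. Give each 5-month rate with a sensitivity range in which non-completers have a higher rate, for example 2 and 3 times that of completers. At 80% completion these multiply the observed rate by 0.8 + 0.2 × 2 = 1.2 and 0.8 + 0.2 × 3 = 1.4.

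The cost is SAP wording and modest extra analysis, with no new data. The downside is a wider stated range for the violence rates.

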## 1.2 SCHEMA

## 1.3 SCHEDULE OF ACTIVITIES (SOA)

Procedures	Preparation before recruitment	Baseline	1-month follow-up	5-month follow-up	Post-study semi-structured interviews
Randomization by residence hall	X				
Demographics		X	X	X	
Sexual and Intimate Partner Violence Knowledge		X	X	X	
Self-Efficacy of Protective Behaviors Related to Sexual and Intimate Partner Violence		X	X	X	
Intimate Partner Violence Attitude Scale		X	X	X	
Consensual Sexual Activity		X	X	X	
Sexual Experiences Survey (Victimization and Perpetration)		X	X	X	
Universal Violence Prevention Screening		X	X	X	
System Usability Scale			X	X	
System Acceptability			X	X	
User Data			X	X	
Reaction to content					X
Perceived safety					X
Desirability					X
Willingness for future use					X

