## 4 STUDY DESIGN

### 4.1 OVERALL DESIGN

This project builds on the current momentum to address the primary prevention of sexual violence within United States institutions of higher education as well as the proliferation of web-based applications. A before-and-after quasi-experimental, mixed-method pilot design will be used to gather acceptability and safety data as well efficacy trends. Two residence halls (Alice Lloyd and Couzens) at the University of Michigan will be randomized to receive either: (1) the control arm (n=150) which will receive usual care only (all incoming students receive three programs about healthy relationships and sexual violence including Haven, Relationship Remix, and Change it Up) or (2) the usual care (n=150) described above and the web-based intervention (MKit). We will use cluster-randomization by residence hall (to minimize contamination associated with individual-level randomization of students living in the same residence hall). Following the informed consent process, students in both conditions will complete a baseline survey of xx questions. Baseline measures will include: 1) demographic data (n=12), 2) investigator developed questions on knowledge about sexual and intimate partner violence (n=20) adapted from the Texas Education Program Participant Response Form ([https://www.wcasa.org/file\\_open.php?id=787](https://www.wcasa.org/file_open.php?id=787)), 3) investigator developed questions on self-efficacy (n=15), 4) 34 questions from the Revised Intimate Partner Violence Attitude Scale (Finchman, Cuit, Braithwaite, & Pasley, 2008), 5) investigator developed questions on consensual sex (n=2), 6) 10 items from the Sexual Experiences Survey (SES) will measure past experiences with sexual violence (Koss et al., 2007) and 10 items from the Sexual Experiences Survey (SES) will measure past experiences with perpetration (Koss et al., 2007), and 7) 26 questions from the Universal Violence Prevention Screening Protocol – Adapted questions (Heron, Thompson, Jackson, & Kaslow, 2003). All of these are measures have been validated and used extensively in the United States to measure knowledge and attitudes related to gender-based violence. Following the survey, students in the Intervention group will be given the opportunity to interact with the application at their own pace, choosing which content to view in the order they prefer.

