### 5.5 STRATEGIES FOR RECRUITMENT AND RETENTION

Students from the target sample, first-year University of Michigan college students, will be recruited for the study. Two residence halls (Alice Lloyd and Couzens) at the University of Michigan will be randomized to receive either: (1) the control arm ( $n=150$ ) which will receive usual care only (all incoming students receive three programs about healthy relationships and sexual violence including Haven, Relationship Remix, and Change it Up) or (2) the usual care ( $n=150$ ) described above and the web-based intervention (MKit). We will use cluster-randomization by residence hall (to minimize contamination associated with individual-level randomization of students living in the same residence hall). At the end of the Relationship

Remix program, a brief announcement will be made about the opportunity to participate in a research study about healthy relationships and palm cards will be distributed (see recruitment materials). We will recruit specifically from Relationship Remix to ensure that all experimental and control subjects receive the same primary prevention programming currently in place on campus. Interested students will receive a palm card with a link to either the MKit web-based application (Intervention) with an access code to sign-up for the website, or a link to the baseline consent and Qualtrics survey (Control) without access to the web-based application. At the end of the study, students from each condition will be invited to participate in an in-person semi-structured interview. Students will receive the invitation to participate in the semi-structured interview on the final page of their 5-month follow-up survey. Students who opt to share their email address with the study team at that time will be contacted to set-up an in-person interview based on user status for the intervention (consistent user of MKit, frequent user of MKit, minimal user of MKit) and a diverse group based on gender, race/ethnicity, and age for the control group. Semi-structured interviews will be conducted with participants from both the Control group (n=10) and the Intervention group (n=15).

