#### 9.4.3 ANALYSIS OF THE SECONDARY ENDPOINT

Preliminary analyses of the survey data (knowledge, attitudes, and experiences related to sexual and intimate partner violence) will be analyzed using the Statistical Package for the Social Sciences (SPSS); all p-values will be set at  $<.05$ . Descriptive statistics will be assessed first. The baseline, 1-month post, and 5-month post-intervention tests will be examined for measures of central tendency, measures of dispersion, and frequency distribution on outcomes. Analysis of variance (ANOVA) will be utilized to determine if the scores on the baseline and follow-up tests differ significantly among the two arms. Usability and acceptability scores will be assessed among those in the intervention group.

We are not powered to assess outcome measures; however, we will look at the direction of effects for our outcome measures to allow for power calculations for future scale-up.

---

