#### 9.4.9 EXPLORATORY ANALYSES

We are not powered to assess outcome measures; however, exploratory analyses will be performed to assess the direction of effects for our outcome measures to allow for power calculations for future scale-up.

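### With one residence hall per arm, the between-arm ANOVA at p<.05 cannot test MKit, and the direction of the difference cannot be attributed to it

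*Combined protocol and SAP*

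**What the plan says.** - **Allocation.** Section 4.1: "Two residence halls (Alice Lloyd and Couzens) at the University of Michigan will be randomized to receive either" usual care alone or usual care plus MKit. The schedule in 1.3 lists "Randomization by residence hall", and 5.5 and 6.3 repeat it ("We will use cluster-randomization by residence hall"). The synopsis names the same two halls as the only enrolling sites, with 150 students per group.
- **Test.** Section 9.4.1 sets p<.05 and uses ANOVA "to determine if the scores on the baseline and follow-up tests differ significantly among the two arms". Section 9.4.3 repeats this for knowledge, attitudes and experiences of violence.
- **Use of the result.** Section 9.4.1: "we will look at the direction of effects for our outcome measures to allow for power calculations for a future R-Level submission". Section 9.4.3 has the same aim, "we will look at the direction of effects for our outcome measures to allow for power calculations for future scale-up", as does 9.4.9: "exploratory analyses will be performed to assess the direction of effects for our outcome measures to allow for power calculations for future scale-up".
- **Caveats given.** The study is a pilot, is called quasi-experimental (4.1, 4.2), and is said to lack power for these outcomes. Section 9.4 mentions no hall effect, no ICC, and not the fact that each arm is a single hall.

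**The concern.** Every MKit student lives in one hall and every control student in the other. Any difference between the halls in who lives there, in peer culture or in events during the year appears as an arm difference. The ANOVA judges that difference against variation between students within halls, as if hall did not matter. The protocol's own reason for allocating by hall is contamination between hall-mates, which concedes that students in a hall influence one another.

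Followed as written, the plan can report a hall difference as a significant arm difference, and carry its direction into the next study as if it were the direction of MKit's effect. Section 3 calls supplying inputs for a larger study a key component of this pilot, so that purpose is directly exposed.

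**Working it through.** **Inputs from the documents.** 2 halls, 2 arms, 150 students per hall, nominal level .05 (sidedness not stated; two-sided assumed). There is no planned power figure to reproduce, because 9.2 says no formal calculation was done.

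**What follows with no assumption.** Hall-level error df = 2 − 2 = 0. With one hall per arm, the smallest two-sided randomisation p-value is 1.00. More students per hall change neither figure.

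**Assumptions for size.** Halls are treated as random draws with total score variance 1. The ICC, the number analysed per hall (m), hall stability over time (c), within-student correlation (r) and a true effect of 0.2 SD are all assumed.

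*Single time point.*
- Variance the ANOVA uses: 2(1−ICC)/m
- True variance of the arm difference: 2(ICC + (1−ICC)/m)
- Actual type I error: 2[1 − F(t_crit·√(ANOVA variance/true variance))], where F is the t distribution with 2m−2 df
- Probability of the wrong sign: Φ(−0.2/√true variance)

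Example, m = 150, ICC = .01: ANOVA variance 2(.99)/150 = .0132; true variance 2(.01 + .0066) = .0332; ratio 2.52. The critical value 1.968 shrinks to 1.968/√2.52 ≈ 1.24, giving type I error .216. Wrong sign: Φ(−0.2/.182) = .136.

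| ICC | Type I, m=150 | Type I, m=75 | Wrong sign, m=150 |
|---|---|---|---|
| 0 | .050 | .050 | .042 |
| .001 | .068 | .059 | .053 |
| .005 | .138 | .094 | .095 |
| .01 | .216 | .138 | .136 |
| .05 | .510 | .376 | .276 |

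Simulating 40,000 two-hall trials per setting at m = 150 gave type I error .068, .139, .217 and .514 for the four non-zero ICCs.

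*Arm-by-time.* A stable hall difference cancels; hall-specific change does not.
- Hall variance of change: 2·ICC·(1−c)
- Student variance of change: 2(1−ICC)(1−r)
- True variance of the difference: 2(hall variance + student variance/m)

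Example, m = 150, r = .5, ICC = .05, c = .8: hall .02, student .95. True variance 2(.02 + .95/150) = .0527 against ANOVA variance 2(.95)/150 = .0127, a ratio of 4.16. Type I error is .335 and wrong sign .192.

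| Hall stability c (m=150, r=.5) | Type I, ICC .01 | Type I, ICC .05 | Wrong sign, ICC .01 | Wrong sign, ICC .05 |
|---|---|---|---|---|
| 1 | .050 | .050 | .041 | .038 |
| .95 | .068 | .142 | .052 | .092 |
| .8 | .122 | .335 | .085 | .192 |

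Varying r from .3 to .7 moves the type I error at c = .8 to .101–.166 (ICC .01) and .276–.432 (ICC .05).

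**The case against.** The plan never says that a significant difference would prove MKit works. Section 9.1 speaks of exploring preliminary differences, 9.4.9 is exploratory, the lack of power is stated repeatedly, and quasi-experimental is a recognised warning about causal attribution. If the two halls are taken as fixed, the ANOVA is a reasonable test of whether their students differ. The inflation figures need halls to be random and rest on assumed values, and on the before-and-after reading there may be no inflation at all. Nor does the sign of an effect enter a power formula.

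Part of this stands. Only the zero degrees of freedom is firm; the rest is illustration, and the normal-score model may fit the victimisation and perpetration items poorly. But a test that two halls differ is not a test of MKit, and 4.2 says the design will measure preliminary efficacy. Low power is a statement about precision, and the quasi-experimental label does not tell the reader that hall and arm cannot be separated. Baseline data help only against stable hall differences, and no change-score or arm-by-time model is specified. If direction does not enter a power formula, the stated purpose needs rewording anyway, and a magnitude taken from the same contrast would be confounded in the same way.

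The subgroup comparisons in 9.4.7 and the retention comparison in 9.1 share the confounding. The general approach in 9.4.1 governs the subgroup tests, and descriptive reporting still satisfies 9.1.

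**Conclusion.** The concern holds and should be fixed. That hall and arm are inseparable follows from the documents alone and cannot be repaired by a mixed model, GEE or robust standard errors. The practical size is unknown: across the main assumptions (m = 150, ICC .001 to .05), the nominal 5% test has an actual error of about 7% to 51% at one time point. On the arm-by-time reading with r = .5 and ICC .01 to .05, it runs from 5% to about 34%. This design cannot show where in those ranges it lies.

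The consequence is confined to the secondary between-arm comparisons. Usability and acceptability are assessed within the intervention group, and safety and willingness come from interviews, so the primary endpoints in 9.4.2 are unaffected.

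**What to change.** 1. **Sections 9.4.1 and 9.4.3.** Remove the between-arm tests at p<.05. State that each arm is one hall, so hall and arm cannot be separated. Report each arm's results and the between-arm difference descriptively. If an interval is shown, label it as within-hall sampling error only, say that it understates the true uncertainty, and do not use it to judge whether MKit has an effect.
2. **Sections 9.4.1, 9.4.3 and 9.4.9.** Replace the direction-of-effects aim with the planning inputs this pilot can supply: outcome SDs, baseline-to-follow-up correlations, event rates and retention, each noted as coming from one hall per arm. State that the effect size, and the ICC if the next trial is clustered, will come from outside this pilot and be varied over a range.

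The cost is wording in three subsections and the loss of p-values that do not validly test MKit. No extra students or halls are needed, and the objectives, hypotheses and sample-size statement can stay. Keeping a hall-level test would instead require more halls. The smallest two-sided p-value in an unmatched randomisation test is 2/6 = .333 with two halls per arm, 2/20 = .100 with three and 2/70 = .029 with four, so at least eight halls would be needed to reach p<.05.
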